9.2 Statistical Methods

Descriptive and frequency statistics will be used to describe the demographic, clinical, and prognostic characteristics of the randomized sample. All inferential analyses will be performed in an "intention-to-treat" fashion. A "per-protocol" analysis will also be performed. For the primary outcome, access site complications, both bivariate (chi-square or Fisher's Exact test) and multivariate (logistic regression) analyses will be performed to compare the two groups. Unadjusted odds ratios (OR) with 95% confidence intervals (95% CI) will be generated for the chi-square analyses and adjusted odds ratios (AOR) with 95% CI will be calculated for the logistic regression analyses. Baseline demographic, clinical, and prognostic characteristics will be compared between the treatment arms using between-subjects inferential analyses after randomization to test for any significant differences. Any significant

differences at baseline will be accounted for in the primary analysis using logistic regression. Chi-square or Fisher's Exact test will be performed to compare the treatment arms on distinguishing extravasation post-closure at the end of the procedure (yes/no), comparing the need for open vascular surgery (yes/no), utilizing a PTA/stent to help with hemostasis or local vascular complications (yes/no), bleeding/hematomas (yes/no), pain or numbness in the distal extremity (yes/no), mortality related to complications associated with the vascular closure site (yes/no), and conversion to general anesthesia due to additional procedures required to address CFA access site complications (yes/no). Cross-tabulation tables with frequencies, percentages, and associated OR with 95% CI will be reported and interpreted for all bivariate analyses of categorical, secondary outcomes. For count variables and non-normal continuous parameters (number of perclose devices, LOS, and serum creatinine), Mann-Whitney U tests will be performed to compare the two treatment arms. Medians and interquartile ranges will be reported and interpreted for the non-parametric analyses of the count and continuous parameters. Survival analysis will be performed using Kaplan-Meier in order to compare the two treatment arms on "time-to-event" outcomes. Mean and median times to events will be presented. Log-rank, Breslow, and Tarone-Ware tests will be used to compare the respective groups. Survival plots will also be graphed. All analyses will be performed using SPSS Version 29 (Armonk, NY: IBM Corp.) and statistical significance will be assumed at an alpha value of 0.05.

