9. STATISTICAL METHODS AND DETERMINATION OF SAMPLE SIZE

9.1 Sample Size Determination

The researchers could not find an evidence-based measure of effect size from the existing literature. Therefore, this project will be considered a pilot study. The researchers believe there will at least be 10-20% reduction in complications associated with the treatment based on clinical experience. An *a priori* sample size calculation was performed using a 20% reduction, and with a two-tailed hypothesis, a power of 80%, and an equal allocation ratio to treatment arms, a total of $n = 100$ participants was generated. Therefore, the researchers plan on enrolling $n = 50$ participants in each treatment arm, totaling $n = 100$ participants. The effect size yielded from the final analysis will be used to power a future, larger trial between the two treatment arms.

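### Section 9.2 gives the adjusted primary odds ratio no sparse-data method: with an assumed 10–20 events it can have no finite value, and it is inflated if several covariates enter; Firth logistic regression handles both

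*Combined protocol and SAP*

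**What the plan says.** Section 9.2 plans two analyses of the primary outcome, access site complications. The first is a chi-square or Fisher's exact test with an unadjusted odds ratio. The second is a logistic regression, for which "adjusted odds ratios (AOR) with 95% CI will be calculated for the logistic regression analyses". Covariates are not listed in advance. Baseline characteristics are tested between arms, and any significant "differences at baseline will be accounted for in the primary analysis using logistic regression". The software is SPSS 29.

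Section 9.2 does not mention a penalised or exact estimation method, a limit on the number of covariates, or what is reported if one arm has no events.

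Section 9.1 explains the sample size. It concedes that "The researchers could not find an evidence-based measure of effect size from the existing literature", reports that the "sample size calculation was performed using a 20% reduction" "with a two-tailed hypothesis, a power of 80%, and an equal allocation ratio to treatment arms", and arrives at 100 patients, 50 per arm. It adds that "The effect size yielded from the final analysis will be used to power a future, larger trial". It gives no control rate, no expected number of events, and no statement of which effect measure is carried forward.

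**The concern.** Ordinary logistic regression relies on large-sample behaviour, and a trial of 100 patients with a fairly uncommon outcome may not provide it. Two things can go wrong.

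- **No estimate.** If one arm has no events, the maximum-likelihood treatment coefficient runs to infinity. The adjusted odds ratio and its interval then cannot be reported. If IVL works well, this happens in the very result most favourable to it.
- **Inflation.** With few events per model parameter, the estimated log odds ratio tends to lie too far from zero.

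An effect size for a later trial is a stated purpose of this pilot, so the quality of the estimate matters as well as the p-value.

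**Working it through.** **1. Inputs.** From the documents: 50 per arm (3.3, 9.1); two-sided test, 80% power, 1:1 allocation (9.1); alpha 0.05 (9.2); a 20% reduction, not said to be absolute or relative (9.1). Assumed: the control rate, and all covariate properties used below.

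**2. What event rates fit N = 100?** For two proportions, with d = p1 − p2 and p̄ their mean:

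n per arm = [1.96·√(2p̄(1−p̄)) + 0.842·√(p1(1−p1) + p2(1−p2))]² / d²

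- 25% vs 5%: (1.96·√0.255 + 0.842·√0.235)² / 0.04 = 1.954 / 0.04 = 48.8, so 49 per arm. Power at 50 per arm is 80.9%.
- 22% vs 2%: 50 per arm with continuity correction.
- 30% vs 10%: 49 per arm only if one-sided, which is not the stated test.
- 50% vs 30%: (1.96·√0.48 + 0.842·√0.46)² / 0.04 ≈ 93 per arm, so high rates do not fit.
- A 20% relative reduction does not fit at plausible rates (20% vs 16% needs 2,894 patients).

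The stated N therefore cannot be reproduced without assuming a control rate. It is consistent with a 20-point absolute drop from roughly 20–30%.

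**3. Expected events** = 50·(p1 + p2): 12 at 22/2, 15 at 25/5 (95% range 9–22), 20 at 30/10. The limiting case 20/0 gives 10. Hence about 10–20.

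**4. Probability that an arm has no events.** This is essentially (1 − p2)^50:

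| Control / IVL rate | P(no finite odds ratio) |
|---|---|
| 30/10 or 20/10 | 0.90^50 = 0.5% |
| 26/6 | 0.94^50 = 4.5% |
| 25/5 or 15/5 | 0.95^50 = 7.7% |
| 22/2 | 0.98^50 = 36% |

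In simulation at 25/5, adding 1–8 covariates left the figure at 7–8.5%.

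As an illustration, take 12/50 control events and 0/50 IVL events. Maximum likelihood gives an odds ratio of 0 with no finite log. Treatment-only Firth is equivalent to adding 0.5 to each cell: (0.5 × 38.5) / (50.5 × 12.5) = 19.25 / 631.25 = 0.030, which is finite.

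**5. Bias among estimable trials.** Figures are the relative error in the treatment log odds ratio. The no-covariate figures are exact enumeration. The others are simulations with independent covariates, either standard normal (log odds ratio 0.5 per SD) or binary with 30% prevalence.

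| Covariates | 25/5 | 20/10 |
|---|---|---|
| 0 | +1.6% | +6.6% |
| 2 (normal) | +5.1% | +7.8% |
| 5 (binary to normal) | +10 to +15% | +15 to +18% |

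Simulations with rarer binary covariates (20% prevalence, odds ratio 1.65) gave similar results, though one put two covariates at 20/10 as high as +11%. With no true effect (15/15) the bias is zero. At 15/5 without covariates it is −0.3%. At 22/2 it runs towards no effect: −15% with none, −7% with three, about 0 with five.

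**6. The plan's own covariate rule.** With 10 independent baseline tests at 0.05, P(none selected) = 0.95^10 = 60%, and P(at most one) = 0.599 + 10 × 0.05 × 0.95^9 = 91%. Simulating the rule with 12 baseline variables selected 0.6 covariates on average. At 25/5 the mean maximum-likelihood log odds ratio was −1.89, against a marginal truth of −1.85 and a fully conditional truth of −1.98. It was not estimable in 7.4% of trials. The SD of the estimate was 0.62–0.68 across 25/5, 30/10 and 20/10.

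**7. Firth in the same settings.** It was finite in every simulated trial and within about 5% of the true log odds ratio at the rates that were not extreme. It shrinks further when the IVL rate is very low: treatment-only, −6% at 22/2 and −14.5% at 21/1. Its SD under the plan's rule was 0.60–0.74.

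**The case against.** The strongest reply is that the plan will rarely fit a large model. That stands: under its own rule none or one covariate usually enters, and the bias is then small beside an SD of about 0.65. It is also fair that this is a declared pilot, that the chi-square or Fisher p-value survives an empty arm, and that the event count is inferred. If the undefined complication outcome proved much more common, the problem would shrink: at 50/30, with 40 events, treatment-only bias is 2.4% and an empty arm essentially never occurs.

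Three stronger readings are tempting, and the documents do not support them.

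- *The estimate is biased away from no effect whichever covariates are used.* The bias depends on how many enter, is nil under no effect, and reverses near a 2% IVL rate. Only the non-estimability is independent of the covariates.
- *The adjusted result fails in a quarter of trials.* With five binary covariates of 20% prevalence, some coefficient diverges in 12–14% of trials at 25/5 and 26–31% at 15/5. The treatment coefficient itself diverges in only about 8%; in the rest, only a covariate coefficient does.
- *The next trial will be 22–32% too small.* Sample size scales roughly as 1/(log OR)², so overstatement of 13–21% gives 1/1.13² = 0.78 to 1/1.21² = 0.68 of the patients needed. That requires five to eight covariates and the adjusted odds ratio being the figure carried forward. Section 9.1 does not name the measure, and it sized this trial on a percentage reduction.

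What the reply does not remove is the empty-arm case. Nothing in 9.2 covers it, and pre-specifying covariates would not cure it. A p-value alone does not supply the effect size that 9.1 wants. The covariate count is also left to the data, so it cannot be known in advance to stay small.

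**Conclusion.** The point holds in a limited form. Under the assumption of a 20-point absolute drop from a 20–30% control rate, the planned adjusted odds ratio rests on about 10–20 events. It has no finite value in roughly 0.5–8% of trials at IVL rates of 10% to 5%, and in 36% at 2%. Inflation of the log odds ratio is a secondary matter: about 0–8% with none to two covariates, and 10–18% if five enter.

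The covariate effects, their independence and the number of baseline variables are assumptions of this check, not figures from the protocol. The empty-arm probabilities depend only on the event rates and 50 per arm. The same gap affects the planned unadjusted odds ratio, which equals the treatment-only model.

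This is a cheap, worthwhile improvement to the estimator. It is not a flaw that invalidates the trial, and no claim about the size of the next trial follows from it without the further conditions above.

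**What to change.** Add to section 9.2:

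> The adjusted primary odds ratio will be estimated by Firth penalised-likelihood logistic regression with a profile penalised-likelihood 95% confidence interval; ordinary maximum likelihood is a sensitivity analysis. If an arm has no events, the unadjusted odds ratio will be estimated by the same method with treatment as the only term.

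If an adjusted effect is carried into the next trial's sample size, name the Firth estimate as the source. Settle this before outcome data are seen, since choosing the estimator after finding an empty cell would be data-driven.

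The cost is SAP wording and possibly a routine beyond base SPSS 29; no patients or data are added. Estimates are shrunk slightly towards no effect, and more so at very low IVL rates. The method does not reduce the sampling uncertainty (SD of the log odds ratio roughly 0.6–0.8), and it does not replace a limit on the number of covariates.

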4. STUDY PROCEDURES

4.1 Screening and Enrollment

Screening assessments will be completed by the study team on a day before the procedure to allow patients time to review and ask questions. Assessments will be initiated after the Informed Consent Form (ICF) Process. A study designee will present the study information to the patient. They will explain the purpose, risk, and benefits to the subject and present them with an IRB approved ICF. The potential participant will be given ample time to read the ICF and all questions and concerns from the subject will be addressed by a study team member. No procedures will be initiated prior to the subject signing and dating the ICF. After the subject signs the ICF, a copy will be given to them for their records. Participants will be informed that they can decline participation in the study without any effect on their health care. They can also withdraw their consent, including the consent to do various screening tests, at any time.

4.2 Datapoints/procedures to be collected/obtained:

- Informed Consent
- Medical History Review for Inclusion/Exclusion Criteria
- Concurrent Medication Review
- Pre-TAVR CT scan review
- Review of pre procedure laboratory results
- Demographics
- Pre-procedure consultation/progress notes
- Post procedure notes (consult, progress, discharge summary)
- Post procedure laboratory results and imaging
- Post discharge follow up office notes and vital signs

If subjects meet all I/E criteria, they will be Enrolled, and the following will be recorded

- Flow rates prior to and post procedures
- Documentation of extravasation post closure at the end of the procedure.
- If open vascular surgery occurred
- Number of perclose devices used

- Bleeding/Hematoma outcomes
- Hospital length of stay
- Renal function lab results post procedure
- Pain or numbness in the distal extremity post procedure
- Whether conversion to General Anesthesia was needed during procedure
- Review of post-procedure laboratory results
- Surgical/procedure reports
- Mortality
- Discharge summary
- Adverse event monitoring

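### Section 9.2 lets chance baseline p-values choose the covariates of the primary analysis, and labels neither the unadjusted nor the adjusted odds ratio as primary

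*Combined protocol and SAP*

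**What the plan says.** For the primary outcome, section 9.2 plans a chi-square or Fisher's exact test and also says that "multivariate (logistic regression) analyses will be performed to compare the two groups". On estimates, "Unadjusted odds ratios (OR) with 95% confidence intervals (95% CI) will be generated for the chi-square analyses", with adjusted odds ratios and intervals from the logistic models. None of these is called the primary analysis.

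The same section then turns to the patients' features at entry, which "will be compared between the treatment arms using between-subjects inferential analyses after randomization to test for any significant differences". The next sentence gives the consequence of a positive test, namely that such "differences at baseline will be accounted for in the primary analysis using logistic regression". The variables to be tested are not listed, no covariate is named elsewhere, and section 4.3.3 names no stratification factor. The only significance level given is general: "statistical significance will be assumed at an alpha value of 0.05". It is taken here as the cut-off for the baseline tests too.

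Section 9.1 gives the expected effect ("The researchers believe there will at least be 10-20% reduction in complications associated with the treatment based on clinical experience"), sizes the trial on the 20% figure, and adds: "The effect size yielded from the final analysis will be used to power a future, larger trial between the two treatment arms". It does not say whether that effect size is the unadjusted or the adjusted one.

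**The concern.** If allocation is properly random, a significant baseline difference is a chance finding. A test for it says nothing about whether the variable predicts complications. Choosing covariates this way makes the content of the primary model depend on the luck of the draw, and it usually leaves out the variables for which adjustment would help.

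Two things are at stake. One is definition: before the data are seen, nobody can write down the primary model or say which odds ratio answers the primary question. The other is precision: the rule adds covariates without regard to prognosis, in a trial that may have few events.

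**Working it through.** **Inputs.** From section 9.1: two-sided test, 80% power, 50 per arm, 20% reduction. From section 9.2: alpha 0.05. The documents give no control rate and no variable list, so rates and variable counts below are assumptions. The reduction is read as absolute percentage points.

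**The plan's own figure.** With an assumed 25% vs 5% and the pooled-variance formula, n per arm = [1.96·√(2·0.15·0.85) + 0.84·√(0.25·0.75 + 0.05·0.95)]² / 0.20² = 48.8, so 49 per arm and 98 in total. This is close to the stated 100, so 25% vs 5% is a reasonable scenario. Expected events: 50·0.25 + 50·0.05 = 15.

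**How often the rule acts.** For k independent baseline tests at 0.05, P(at least one enters) = 1 − 0.95^k:
- k = 10: 40%
- k = 15: 54%
- k = 20: 64%

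A given variable, prognostic or not, enters with probability of about 5%.

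**Type I error.** In simulation at 15% vs 15%, the rule (bivariate test if nothing enters, adjusted Wald test if something does) rejects in 4.2–5.3% of trials, against 5.0–6.0% for the unadjusted test.

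**Power by test, without covariates.** Exact binomial enumeration, 50 per arm; chi-square, with Fisher if an expected count is below 5:

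| Assumed rates | Chi-square/Fisher | Wald, zero-event arm counted as non-significant | Wald, bivariate test used for zero-event arm |
|---|---|---|---|
| 25% vs 5% | 84.65% | 73.9% | 81.5% |
| 30% vs 10% | 73.4% | 69.8% | 70.3% |
| 25% vs 15% | 24.4% | 21.8% | 21.8% |

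At 25% vs 5%, the treated arm has no events with probability 0.95^50 = 7.7%. Of the 10.8-point gap between the first two columns, 7.6 points come from those trials and 3.1 remain. On the same scenario a likelihood-ratio test has 85.5% power, and Fisher's test used throughout has 74.8%.

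**Power of the rule.** The change of test costs about 3.1 points at 25% vs 5% and at 30% vs 10%, but only in trials where a covariate enters: 3.1 × 0.40 = 1.2 to 3.1 × 0.64 = 2.0 points. The covariates themselves cost a further 1–2. The sum is about 2–4 points. A direct simulation (4,000 replicates per setting, k independent normal variables, one prognostic with log-OR 0.5 per SD, t-tests for entry) agrees within an error of about half a point:
- 25% vs 5%: losses of 2.5, 3.2 and 4.6 points for k = 10, 15, 20.
- 30% vs 10%: losses of 2.5, 2.6 and 3.7 points.
- 25% vs 15%: a loss of about 1–2 points.
- Likelihood-ratio test in place of Wald: mostly about 1 point or less; the largest value was 1.9 (30% vs 10%, k = 20).

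If zero-event trials are counted as non-significant, the loss at 25% vs 5% becomes 6–10 points.

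**Future trial.** When a covariate enters, the two odds ratios differ by a median factor of 1.10 to 1.23, depending on the covariates assumed. At 25% vs 15%, the formula gives 250 per arm; a factor of 1.10 on the odds ratio moves this to 196 or 335. The pilot's own error is larger: SE(log OR) = √(1/12.5 + 1/37.5 + 1/7.5 + 1/42.5) = 0.513, and the interquartile range of the odds ratio alone, a factor of exp(0.6745 × 0.513) = 1.41 each way, spans 119 to 1,079 per arm.

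**The case against.** The strongest reply is that the rule is stated in advance, uses no outcome data, and sits in a self-declared pilot in which both odds ratios will be reported, so a reader can see any difference. All of that stands, and it is why the harm is modest. It does not say which result is the primary one, and stating a rule in advance does not make it a good way to choose covariates.

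A reader might infer three stronger points that the documents do not support:
- **That baseline p-values switch the primary result from the unadjusted to the adjusted odds ratio.** Section 9.2 states no such switch. An unadjusted result with an adjusted companion is an equally natural reading. What the text does establish is that neither is labelled, and that covariates enter the primary analysis by significance.
- **That 6–10 points of power are lost.** This needs a Wald test, which the plan does not name, and needs zero-event arms counted as failures although the bivariate test is planned and would nearly always be significant there. Moreover, most of that loss comes from the Wald test with few events, not from baseline testing, and a pre-specified Wald model would share it. Against Fisher throughout (74.8%), which the plan's wording permits, a change to Wald (73.9%) costs almost nothing.
- **That the next trial would be badly sized.** The gap between the two odds ratios is small beside the pilot's sampling error. Naming one is a matter of clarity.

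**Conclusion.** The point holds in a limited form. Section 9.2 selects covariates for the primary analysis by baseline significance, which tracks chance imbalance, and leaves the primary estimate unlabelled. With 10–20 independent variables the rule acts in 40–64% of trials, yet picks up any given prognostic variable about 5% of the time. It therefore makes the model unpredictable and buys little precision.

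There is no type I error inflation. The power loss is conditional: about 2–4 points under a Wald test at 25% vs 5% or 30% vs 10% with the bivariate test covering zero-event arms, and about 0–1 point (at most about 2 in the settings run) with a likelihood-ratio test. These figures rest on assumed rates, assumed independent variables, and a reading in which the adjusted test is used whenever a covariate enters. The case for change rests mainly on having a defined primary analysis, and the change is cheap.

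**What to change.** In section 9.2, delete the baseline significance tests and the rule that adjusts for significant differences; describe baseline characteristics by arm only. Name one intention-to-treat primary analysis in advance. Either choice cures the defect:
- the unadjusted comparison, stating now when chi-square and when Fisher applies (at 25% vs 5% that choice is worth about 10 points: 84.65% vs 74.8%); or
- a logistic model with one or two covariates chosen for expected prognosis, with a likelihood-ratio or penalised method if events are few.

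Report the other as supportive. In section 9.1, state that the named primary estimate, with its confidence interval, is the effect size carried to the future trial.

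The cost is SAP wording and possibly one case report form field. If the CT calcium arc is chosen as a covariate, its value must be recorded: section 4.2 lists "Pre-TAVR CT scan review", but section 3.4.1 needs only a threshold. The team should confirm that the named SPSS version offers the chosen method. The trade-offs are these: an unadjusted primary gives up precision from a strong covariate, an adjusted one uses up a little information when events are few, and a chance imbalance is addressed only in supportive analysis.

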3.2.2 Secondary Objectives

1. Determine the clinical outcomes between groups.
2. Distinguish extravasation post closure at the end of the procedure.
3. Compare the need for open vascular surgery between groups.

4. Examine PTA or Stents to the CFA to help hemostasis or local vascular complications between groups.
5. Number of Perclose devices used between groups.
6. Compare Bleeding/Hematoma between groups.
7. Examine the difference in hospital length of stay between groups.
8. Examine renal function post procedure
9. Difference in pain or numbness in the distal extremity between groups
10. Mortality related to complications from vascular closure site between groups.
11. Conversion to general anesthesia due to additional procedures required to address the CFA access site complications between groups.

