5.2 Intervention Risk

There is the potential risk of an interventional failure for study participants. The study results may not support the primary hypothesis that in patients with severely calcified femoral arteries, a pre-treatment with Shockwave intravascular lithotripsy intervention will not result in a decrease in femoral artery access site complications. It is possible that the intervention will prove to be less effective than the current standard method in which Shockwave intravascular lithotripsy is not used prior to access and placement of the TAVR delivery system.

Indications for Use—The Shockwave Medical Intravascular Lithotripsy (IVL) System is intended for lithotripsy-enhanced balloon dilatation of lesions, including calcified lesions, in the peripheral vasculature, including the iliac, femoral, ilio-femoral, popliteal, infra-popliteal, and renal arteries. Not for use in the coronary or cerebral vasculature.

Contraindications—Do not use if unable to pass 0.014" (M5, M5+, S4) or 0.018" (L6) guidewire across the lesion-Not intended for treatment of in-stent restenosis or in coronary, carotid, or cerebrovascular arteries.

Adverse effects—Possible adverse effects consistent with standard angioplasty include:

- Access site complications
- Allergy to contrast or blood thinner
- Arterial bypass surgery

- Bleeding complications
- Death
- Fracture of guidewire or device
- Hypertension/Hypotension
- Infection/sepsis
- Placement of a stent
- renal failure
- Shock/pulmonary edema
- target vessel stenosis or occlusion
- Vascular complications
- Risks unique to the device: device malfunction or failure
- Excess heat at target site.
- Allergic/immunologic reaction to the catheter material(s) or coating-Device malfunction failure, or balloon loss of pressure leading to device embolism, dissection, serious injury or surgical intervention
- Atrial or ventricular extrasystole-Atrial or ventricular capture

5.3 Psychological Risks:

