7. ENDPOINTS/OUTCOMES

7.1 Efficacy

1. Evaluate for contrast extravasation post closure of femoral artery at the end of the procedure
2. Determine need for Vascular surgery consultation
3. If vascular complication, was PTA, stenting, or open surgery used
4. Number of perclose devices used to close the femoral artery access site
5. Determine presence of other vascular complications i.e. bleeding, hematoma, emboli etc.
6. Review lab values and vital signs to determine if there is any clinical deterioration (drop in hemoglobin, worsening of creatinine, development of hypotension/shock, infections/sepsis)
7. Determine if there is a difference between hospital length of stay
8. Assess for difference in pain/numbness in distal extremities post-procedure
9. Assess for differences in mortality related to complications between the groups
10. Failure of treatment

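### Section 9.2 compares the arms only on closure-site-attributed death and access-site-attributed conversion to general anesthesia; no named analysis shows total deaths or total conversions by arm

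*Combined protocol and SAP*

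**What the plan says.** **Collected.** The list in section 4.2 includes mortality, with no limit on cause, and "Whether conversion to General Anesthesia was needed during procedure", with no limit on reason.

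**Compared.** Secondary objective 10 in section 3.2.2 is "Mortality related to complications from vascular closure site between groups". Objective 11 is "Conversion to general anesthesia due to additional procedures required to address the CFA access site complications between groups". Section 9.2 carries both into chi-square or Fisher tests as "mortality related to complications associated with the vascular closure site (yes/no), and conversion to general anesthesia due to additional procedures required" to deal with CFA access-site complications.

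**A third wording.** Item 9 of section 7.1 reads "Assess for differences in mortality related to complications between the groups". It is not tied to the closure site, but it still depends on attribution. Section 7.1 does not list conversion to general anesthesia.

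**Attribution and safety.** Under section 8 the investigators attribute adverse events by clinical judgment, and only events at least possibly related go into the CRFs. A serious event put down to an unrelated pre-existing condition is not documented as an SAE. The AE and SAE counts in section 7.2 cover related events only, and 9.2 names no between-arm analysis of them.

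**Time to event.** Section 9.2 plans Kaplan-Meier curves and three tests but does not name the events.

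**The concern.** Whether a patient died needs no judgment. Whether a death was related to the vascular closure site does. The plan collects the first and compares only the second. It gives no rule for relatedness, describes no masking of whoever decides, and provides no independent adjudication. The treating team knows who had IVL.

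The filter applies to both arms, but only Group 1 receives IVL. Section 5.2 lists hazards of the device that need not present at the closure site, among them device embolism after loss of balloon pressure and "Atrial or ventricular extrasystole-Atrial or ventricular capture". A death by such a route could be absent from the one mortality comparison that 9.2 names. At stake is whether a reader of the pilot, and the designers of the larger trial that it is meant to inform (section 9.1), can see how many patients died in each randomized arm without relying on an open-label classification.

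**Working it through.** This is mainly a comparison of text.

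**Step 1: what is recorded against what is compared.**

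| Outcome | 4.2 (recorded) | 3.2.2 (objective) | 7.1 (endpoint) | 9.2 (named comparison) |
|---|---|---|---|---|
| Death | any | closure-site related | related to complications | closure-site related |
| Conversion to general anesthesia | any | due to CFA access-site procedures | not listed | due to CFA access-site procedures |

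The 9.2 column contains neither all-cause death nor any-reason conversion.

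**Step 2: where else a death unrelated to the closure site could surface.**
- Section 7.1 item 9: possibly, if it is judged to follow a complication. Section 9.2 has no matching analysis.
- Section 7.2: only if judged related to the study procedure, and with no between-arm analysis named.
- Section 8: not as an SAE if put down to an unrelated pre-existing condition.
- Kaplan-Meier in 9.2: possibly, but no event is named.

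Each route depends on attribution or is unspecified, so none guarantees a count of total deaths by arm.

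**Step 3: what an all-cause comparison could show at 50 per arm.** The group size is from section 9.1. For k deaths in one arm and none in the other, the two-sided Fisher value is p = 2 × C(50,k) / C(100,k).
- k = 1: 2 × 50/100 = 1.0
- k = 3: 2 × 19,600/161,700 = 0.24
- k = 5: 0.056
- k = 6: 2 × 15,890,700/1,192,052,400 = 0.027

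Six against none is the smallest such split below 0.05. Exact Fisher power, by enumerating two binomials at 50 per arm with assumed death rates, is under 1% for 4% vs 2%, 3% for 6% vs 2%, and 19% for 10% vs 2%. With 0 of 50 deaths, the upper limit of the exact two-sided 95% interval is 1 − 0.025^(1/50) = 7.1%. The comparison must therefore be descriptive.

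**Step 4: what reclassification can do.** With assumed counts of 6 vs 0, judging three of the six unrelated to the closure site turns p = 0.027 into p = 0.24. Moving one death between 0 vs 0 and 1 vs 0 changes no inference (p = 1.0). These counts show the mechanism only. They say nothing about its likelihood or direction.

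**The case against.** The attributed outcomes are those an access-site pilot would choose. They match objectives 10 and 11 exactly, and all-cause counts bring in TAVR events that dilute an access-site effect. This stands. It is a reason to keep the attributed versions and not to rank the all-cause ones above them.

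A reader might infer that no planned analysis could ever use total deaths. That goes too far. Item 9 of 7.1 is wider than 9.2, related deaths would enter the SAE count, and the unnamed time-to-event outcomes do not exclude all-cause death. What can be said is that no named analysis commits to it.

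A reader might also infer that deaths from every hazard in 5.2 are IVL deaths that drop out. The documents do not support that. The list is introduced as effects in line with standard angioplasty. Section 5.1 ascribes kidney deterioration, infection, vascular complications, stroke and death to TAVR itself, so these arise in both arms. Section 4.3.3 places the balloon in the CFA that then takes the large-bore sheath, so a dissection there could well be classed as an access-site event. Device embolism and arrhythmia are the clearer examples, and no frequency is given for either.

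Finally, the data are not fully in hand. Section 4.2 gives no time window for mortality, and the 3-month follow-up in section 3.3 is for adverse events. That also stands and belongs in the cost.

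**Conclusion.** The concern holds as a gap in what is reported. Total deaths and total conversions are to be recorded, but the between-arm comparisons named in 9.2 use only versions that depend on attribution with no masking described. A death in either arm judged unrelated to the closure site is a non-event there, and the related-only safety counts and unnamed Kaplan-Meier outcomes do not close the gap.

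Its size cannot be estimated, because the documents give no mortality rate, conversion rate or attributable share. It is tempting to conclude that the restricted outcome favors IVL. The documents do not show this: deaths are filtered in both arms, and nothing indicates how many IVL deaths would arise away from the closure site.

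The conclusion assumes that the section 8 process, the only attribution process described, also governs these outcomes; 9.2 does not say who decides. It is an inexpensive improvement that should be made, not a flaw that undermines the trial.

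**What to change.** In section 9.2:
- Add all-cause death through 3 months and any conversion to general anesthesia, by randomized arm. Give counts, percentages and the difference with an exact 95% confidence interval (method named), and label them descriptive. Place them beside the attributed versions, which stay.
- Name all-cause death as one of the Kaplan-Meier outcomes.
- List each death with arm, day and cause.

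Reconcile the mortality wording across 3.2.2, 7.1 and 9.2.

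**Cost.** Two added outcomes in the tables, one curve and one listing. Vital status must be confirmed for every patient at the planned 3-month follow-up, which 4.2 does not now require explicitly. Because section 11.2 omits missing data, the report should state how many patients have known status. The new counts will include TAVR-related events and will be too few for a powered test.
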